### 8.5. Pharmacokinetics

At the visits and times specified in the Schedule of Activities (Appendix 2), venous blood samples of approximately 2.5 mL each will be collected to determine the serum concentrations of LY2951742. A maximum of 3 samples may be collected at additional time points during the study if warranted and agreed upon between both the investigator and sponsor. Instructions for the collection and handling of blood samples will be provided by the sponsor.

When a blood sample is collected, the time and date of last dose administration prior to blood sampling should be recorded. The actual date and time (24-hour clock time) of each sampling will be recorded. LY2951742 concentration information that may/would unblind the study will

not be reported to investigative sites or blinded personnel until the study has been unblinded. Bioanalytical samples collected to measure investigational product concentration will be retained for a maximum of 1 year following last patient visit for the study.

A validated assay will be used to determine serum LY2951742 concentrations. Samples will be analyzed at a laboratory approved by the sponsor.

It is intended that blood samples collected from patients who received placebo should not be analyzed for determination of serum concentrations of LY2951742.

# 8.6. Pharmacodynamics

At the visits and times specified in the Schedule of Activities (Appendix 2), venous blood samples will be collected to determine the plasma concentrations of CGRP. A maximum of 3 samples may be collected at additional time points during the study if warranted and agreed upon between both the investigator and sponsor. Instructions for the collection and handling of blood samples will be provided by the sponsor. When a blood sample is collected, the time and date of last dose administration prior to blood sampling should be recorded. The actual date and time (24-hour clock time) of each sampling will be recorded.

A validated LY2951742-tolerant assay will be used to determine plasma CGRP concentrations. Samples will be analyzed at a laboratory approved by the sponsor.

Plasma CGRP concentration information that may/would unblind the study will not be reported to investigative sites or blinded personnel until the study has been unblinded.

Bioanalytical samples collected to measure CGRP will be identified by the patient number (coded) and retained for a maximum of 1 year following last patient visit for the study at a facility selected by the sponsor.

### 8.8. Biomarkers

Blood samples for non-genetic biomarker research will be collected at the times specified in the Schedule of Activities (Appendix 2), where local regulations and ERBs allow.

Samples will be used for research on the drug target, disease process, pathways associated with migraine headache and/or other pain conditions, mechanism of action of LY2951742, and/or research method or in validating diagnostic tools or assay(s) related to migraine headache and/or other pain conditions.

All biomarker samples will be coded with the patient number. These samples and any data generated can be linked back to the patient only by the investigator site personnel. Samples will be destroyed according to a process consistent with local regulations.

Samples will be retained for a maximum 15 years after the last patient visit for the study, or for a shorter period if local regulations and ERBs impose shorter time limits, at a facility selected by the sponsor. This retention period enables use of new technologies, response to regulatory questions, and investigation of variable response that may not be observed until later in drug development or when the drug is commercially available.

# 8.8.1. Samples for Immunogenicity Research

Where local regulations and ERBs allow, blood samples for immunogenicity testing will be collected to determine antibody production against LY2951742 as specified in the Schedule of Activities (Appendix 2). Immunogenicity will be assessed by a validated assay designed to detect anti-drug antibodies in the presence of the investigational product. Antibodies may be further characterized and/or evaluated for their ability to neutralize the activity of LY2951742.

Samples will be retained for a maximum of 15 years after the last patient visit for the study, or for a shorter period if regulations and ERBs impose shorter time limits, at a facility selected by the sponsor. The duration allows the sponsor to respond to future regulatory requests related to LY2951742.

### 8.9. Health Economics

Health economic, disability and quality of life assessments of LY2951742 in patients with migraine will be based on the following scales:

Migraine Disability Assessment test (MIDAS): The MIDAS was designed to quantify headache-related disability over a 3-month period. This instrument consists of five items that

reflect the number of days reported as missing, or with reduced productivity at work or home and social events; a higher value is indicative of more disability (Stewart 1999; Stewart 2001). This instrument is considered highly reliable and valid; and is correlated with clinical judgment regarding the need for medical care (Stewart 1999; Stewart 2001).

Migraine Specific Quality of Life questionnaire (MSQ v2.1): The MSQ v2.1 is a self-administered health status instrument, and was developed to address physical and emotional limitations of specific concern to individuals suffering from migraine headaches. The instrument consists of 14 items that address 3 domains: (1) Role Function-Restrictive; (2) Role Function-Preventive; and, (3) Emotional Function (Jhingran 1998). The instrument was designed with a 4-week recall period, and is considered reliable, valid and sensitive to change in migraine (Jhingran 1998; Rendas-Baum 2013). Clinically meaningful differences for each domain have been established and are widely used in the literature.

# 9. Statistical Considerations and Data Analysis

# 9.1. Determination of Sample Size

The study will enroll approximately 825 patients. Eligible patients will be randomized in blinded fashion in a 2:1:1 ratio to placebo (target of 413 patients), LY2951742 120 mg/month (target of 206 patients), or 240 mg/month (target of 206 patients). With the assumption of a 26% discontinuation rate and an effect size of 0.33, it is estimated that this sample size will provide approximately 95% power that at least 1 dose of LY2951742 will separate from placebo at a two-sided significance level of 0.05 based on simulations using Dunnett (Dunnett 1955) test. Assumptions in the simulations were based on data from two double-blind, placebo-controlled, Phase 2 studies, with adjustment to reflect the longer treatment duration and greater variability expected in a larger, multi-country Phase 3 study.

Approximately 100 sites in 11 countries are planned for inclusion in Study CGAH, with an average of approximately 8 patients to be randomized at each investigative site. The final number of sites, countries, and patients per site may vary depending on sites' enrollment rates. Approximately 1557 patients may be screened to ensure randomization of 825 patients, with an estimated 611 patients completing the study.

### 9.2. General Statistical Considerations

Statistical analysis of this study will be the responsibility of Lilly or its designee. Details of statistical analysis methods will be described in the statistical analysis plan (SAP) document.

Unless otherwise specified, analyses will be conducted on an intent-to-treat (ITT) population, which will include all patients who are randomized and receive at least one dose of investigational product. Patients in the ITT population will be analyzed according to the treatment group to which they are randomized. When change from baseline is assessed, the patient will be included in the analysis only if he/she has a baseline and a postbaseline measurement.

The primary analysis will be performed using a restricted maximum likelihood-based mixed models repeated measures (MMRM) technique with prespecified model terms (Section 9.4.1).

Visitwise binary efficacy variables will be analyzed using a generalized linear mixed model (GLIMMIX) as pseudo-likelihood-based mixed effects repeated measures analysis.

In addition to the MMRM approach, analysis of covariance (ANCOVA) model or analysis of variance (ANOVA) with the last observation carried forward (LOCF) will also be implemented. When an ANCOVA model is used to analyze a continuous variable, the model will contain the main effects of treatment and region, as well as the continuous fixed covariates of baseline. The ANOVA model will use the same terms except the continuous fixed covariate of baseline. Type III sum-of-squares for the least-squares means will be used for the statistical comparisons.

Continuous efficacy and health outcome endpoints will be analyzed using MMRM methods, as well as an ANCOVA model with LOCF imputation if deemed appropriate.

Categorical comparisons between treatment groups will be performed using Cochran-Mantel-Haenszel (CMH) controlling for region or using the Fisher's exact test, where appropriate.

Patients will be pooled within each region for statistical analysis purposes. Region will be defined in the SAP.

All tests of treatment effects will be conducted at a 2-sided alpha level of 0.05, unless otherwise stated.

Any change to the data analysis methods described in the protocol will require an amendment ONLY if it changes a principal feature of the protocol. Any other change to the data analysis methods described in the protocol, and the justification for making the change, will be described in the clinical study report or SAP. Changes may only be made in the SAP prior to unblinding. Additional exploratory analyses of the data will be conducted as deemed appropriate.

# 9.3. Treatment Group Comparability

# 9.3.1. Patient Disposition

The number and percentage of ITT patients who complete the study or discontinue early will be summarized for all treatment groups for Study Period III (double-blind treatment) and Study Period IV (post-treatment follow-up) both overall and by visit.

Patient allocation by investigator will be summarized for Study Period III for all ITT patients. Patient allocation by investigator will also be listed for all study periods.

### 9.3.2. Patient Characteristics

The following patient characteristics at baseline will be summarized by treatment group for all ITT patients:

- Demographic (age, gender, ethnic origin, height, weight, body mass index)
- Migraine headache, headache, variation of migraine/headache measures per 30day baseline period.
- Alcohol, tobacco, caffeine and nicotine consumption
- Medical history and pre-existing condition

Medical history and pre-existing conditions will be summarized by preferred term within system organ class (SOC).

# 9.3.3. Concomitant Therapy

The proportion of patients who received concomitant medication (as recorded via eCRF) as well as abortive medications (recorded through ePRO) will be summarized for all ITT patients for Study Period III and Study Period IV separately.

# 9.3.4. Treatment Compliance

Not applicable.

# 9.3.5. Electronic Patient-reported Outcome Diary Compliance

ePRO diary compliance at each period (including baseline, Month 1, 2, 3, ... till Month 10) will be calculated. Diary compliance at each period is calculated as:

Actual number of diary days in the period Expected number of diary days in the period \* 100

Actual number of diary days is calculated as the total number of days with non-missing answers.

# 9.4. Primary and Secondary Analyses

# 9.4.1. Primary Analyses

The primary efficacy measure is the overall mean change from the baseline period in the number of monthly migraine headache day during the 6-month double-blind treatment phase, and the primary analysis will evaluate the efficacy of LY2951742 (120 or 240 mg/month) compared with placebo.

The primary analysis will be performed using a restricted maximum likelihood-based MMRM technique. The analysis will include the fixed categorical effects of treatment, region, month, and treatment-by-month interaction, as well as the continuous fixed covariates of baseline number of migraine headache days and baseline number of migraine headache days-by-month interaction.

An unstructured covariance structure will be used to model within-patient errors. The Kenward-Roger (Kenward and Roger 1997) approximation will be used to estimate denominator degrees of freedom. If the model does not converge with both the Hessian and the G matrix being positive definite under the default fitting algorithm used by PROC MIXED, the Fisher scoring algorithm will be implemented by specifying the SCORING option in SAS. If the model still fails to converge, the model will be fit using covariance matrices of the following order specified by a decreasing number of covariance parameters until convergence is met:

- Heterogeneous Toeplitz
- Heterogeneous First-order autoregressive
- Toeplitz
- First-order autoregressive

When the unstructured covariance matrix is not utilized, the sandwich estimator (Diggle and Kenward 1994) will be used to estimate the standard errors of the fixed effects parameters. The sandwich estimator is implemented by specifying the EMPIRICAL option in SAS®. When the sandwich estimator is utilized, the Kenward-Roger approximation for denominator degrees of freedom cannot be used. Instead, the denominator degrees of freedom will be partitioned into between-subject and within-subject portions by the DDFM=BETWITHIN option in SAS®. SAS® PROC MIXED will be used to perform the analysis.

# 9.4.2. Key Secondary Analyses

The key secondary objectives (see Table CGAH.1) will be tested using an appropriate multiple testing approach providing strong control of the familywise error rate (for the primary and key secondary tests) at a one-sided 0.025 alpha level (or, equivalently, two-sided 0.05 alpha level).

There will be no adjustments for multiplicity for analyses of other endpoints. If the multiple testing approach for key secondary measures only needs to be changed, the updated approach will be provided in the SAP, and it should not lead to modification of this protocol.

The key secondary measures will be analyzed for the double-blind treatment (Study Period III).

For the continuous key secondary measures, the change from baseline during the 6-month double-blind treatment phase will be analyzed from repeated measures analyses as described in Section 9.4.1. For the analysis of 50%, 75%, and 100% response, the percentage of patients meeting response criteria during the 6-month double-blind treatment phase will be estimated for each treatment from a categorical, pseudo-likelihood-based repeated measures analysis of longitudinal binary outcomes indicating whether patients meet response criteria.

This analysis will be implemented using the GLIMMIX procedure in SAS.

# 9.4.3. Other Secondary and Tertiary Efficacy Analyses

The other secondary and exploratory efficacy analyses will be conducted for the double-blind treatment phase, and for the double-blind treatment and post-treatment follow-up phases (Study Period III and Study Period IV) combined. Further details regarding other secondary and tertiary efficacy analyses are summarized in the SAP.

# 9.5. Safety Analyses

The safety analyses will be conducted for the double-blind treatment and post-treatment follow-up phases, as well as the two periods combined. For the two phases combined, only repeated measures and time-to-event analyses will be conducted.

The safety and tolerability of treatment will be assessed by summarizing the following:

- adverse events
  - o treatment-emergent adverse events (TEAEs)
    - by preferred term
    - by SOC
    - by maximum severity
    - by outcome
    - considered to be related to investigational product by investigator
  - serious adverse event
  - o adverse event leading to discontinuation
- Suicidal ideation and behaviors assessed by solicited questioning using the C-SSRS
- Vital signs and weight
- electrocardiograms
- Laboratory measurements
- Anti-LY2951742 antibody

# 9.5.1. Categorical Safety Variables

Unless specified otherwise, the categorical safety analyses will include both schedule and unscheduled visits.

Comparisons between treatment groups for all categorical safety measures will be made using the Fisher's exact test for Study Period III (double-blind treatment) with the ITT population. Descriptive statistics only will be presented for the treatment groups in the post-treatment follow-up phase (Study Period IV) with the post-treatment population.

#### 9.5.2. Adverse Events

Treatment-emergent adverse events are defined as the reported AEs that first occurred or worsened during the postbaseline phase compared with baseline phase. For each TEAE, the severity level of the event (mild, moderate, or severe) will be determined by patient or physician opinion. The Medical Dictionary for Regulatory Activities (MedDRA) Lowest Level Term will be used in the treatment-emergent computation. For each Lowest Level Term, the maximum severity at baseline will be used as the baseline severity. If the maximum severity during

postbaseline is greater than the maximum baseline severity, the event is considered to be treatment-emergent for the specific postbaseline period. For each patient and TEAE, the maximum severity for the MedDRA level being displayed (PT, High Level Term, or SOC) is the maximum postbaseline severity observed from all associated Lowest Level Terms mapping to that MedDRA level.

For events that are gender-specific, the denominator and computation of the percentage will include only patients from the given gender.

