#### 8.2. Adverse Events

Investigators are responsible for monitoring the safety of patients who have entered this study and for alerting Lilly or its designee to any event that seems unusual, even if this event may be considered an unanticipated benefit to the patient.

The investigator is responsible for the appropriate medical care of patients during the study.

Investigators must document their review of each laboratory safety report.

The investigator remains responsible for following, through an appropriate health care option, AEs that are serious or otherwise medically important, considered related to the investigational product or the study, or that caused the patient to discontinue the investigational product before completing the study. The patient should be followed until the event resolves, stabilizes with appropriate diagnostic evaluation, or is reasonably explained. The frequency of follow-up evaluations of the AE is left to the discretion of the investigator.

Lack of drug effect is not an AE in clinical studies, because the purpose of the clinical study is to establish treatment effect.

After the ICF is signed, study site personnel will record via eCRF the occurrence and nature of each patient's pre-existing condition(s), including clinically significant signs and symptoms of the disease under treatment in the study. In addition, site personnel will record via eCRF any change in the condition(s) and any new condition(s) as AEs. Investigators should record their assessment of the potential relatedness of each AE to protocol procedure or investigational product via eCRF.

The investigator will decide whether he or she interprets the observed AEs as reasonably possibly related to migraine headache, to the investigational product, study device, study procedure, or other concomitant treatment or pathologies.

The investigator will answer yes/no when making this assessment.

Planned surgeries and nonsurgical interventions should not be reported as AEs unless the underlying medical condition has worsened during the course of the study.

If a patient's investigational product is discontinued as a result of an AE, study site personnel must report this to Lilly or its designee via eCRF, clarifying if possible, the circumstances leading to discontinuations of treatment.

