5.5.12.1.1. Adverse Events

Treatment-emergent adverse events are defined as the reported AEs that first occurred or worsened during the post-baseline phase compared with baseline phase. For each TEAE, the severity level of the event (mild, moderate, or severe) will be determined by patient or physician opinion. The MedDRA Lowest Level Term (LLT) will be used in the treatment emergent computation. For each LLT, the maximum severity at baseline will be used as the baseline severity. If the maximum severity during post-baseline is greater than the maximum baseline severity, the event is considered to be treatment emergent for the specific post-baseline period. For each patient and TEAE, the maximum severity for the MedDRA level being displayed (PT, High Level Term, or SOC) is the maximum post-baseline severity observed from all associated LLTs mapping to that MedDRA level.

For events that are gender-specific, the denominator and computation of the percentage will include only patients from the specific gender.

Adverse event leading to discontinuation will also be summarized.

5.5.12.1.1.1. Potential Hypersensitivity Events

Potential hypersensitivity events (immediate and nonimmediate) will be identified from a review of preferred terms generated from the following queries:

- Anaphylactic reaction Standard MedDRA Query (SMQ)(20000021)
- Broad and narrow terms in the Angioedema SMQ (20000024)
- Broad and narrow terms in the Hypersensitivity SMQ(20000214)

A listing of patients having an event identified from these analyses will be medically reviewed to determine if the terms identified represent actual hypersensitivity events. Listings should include information on timing of event relative to last administered dose of study drug, the event term from this query, other AEs for the patient and timing, any abnormal laboratory findings, medical history, and anti-drug antibody test results including titer. Only those that are judged medically to be hypersensitivity events will be included in the final tables.

The number and percentage of patients with TEAEs, SAEs, and AEs resulting in study drug discontinuation will be summarized by treatment groups using MedDRA PT nested within the SMQ. Events will be ordered by decreasing frequency within the SMQ.

The number and percentage of patients with treatment-emergent hypersensitivity events by maximum severity will be summarized by treatment groups using MedDRA PT.

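### The severity displayed for a TEAE is the maximum over all LLTs under the term, with no stated limit to the treatment-emergent ones

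*Protocol*

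**What the plan says.** Protocol 9.5.2 builds the display in two steps.

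**Emergence, per LLT.** The MedDRA "Lowest Level Term will be used in the treatment-emergent computation". The comparator is set term by term: "For each Lowest Level Term, the maximum severity at baseline will be used as the baseline severity". If the maximum during "postbaseline is greater than the maximum baseline severity, the event is considered to be treatment-emergent for the specific postbaseline period". Severity has three grades: "the severity level of the event (mild, moderate, or severe) will be determined by patient or physician opinion".

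**Displayed severity, per higher-level term.** The sentence opens "For each patient and TEAE, the maximum severity for the MedDRA level being displayed (PT, High Level Term, or SOC" and ends by saying that this "is the maximum postbaseline severity observed from all associated Lowest Level Terms mapping to that MedDRA level".

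SAP 5.5.12.1.1 keeps both steps; its severity "is the maximum post-baseline severity observed from all associated LLTs mapping to that MedDRA level". SAP 5.5.12.1.1.2 (injection-site events) and 5.5.12.1.1.3 (upper respiratory tract infections) repeat the second step at PT level. Their versions of that sentence refer to adverse events or infection events and do not use the term TEAE.

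Protocol 8.2 has sites record pre-existing conditions, "including clinically significant signs and symptoms of the disease under treatment in the study", and then record changes in those conditions, and new conditions, as adverse events. SAP Table 5.5 sets the TEAE baseline as Visits 1 to 3 for Study Period III and Visits 1 to 12 for Study Period IV.

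**The concern.** The two steps use different sets of terms. The first selects the LLTs that emerged. The second takes its maximum over a set defined by position in the MedDRA hierarchy, whether or not each LLT emerged. An LLT that failed the emergence test can therefore supply the severity printed beside a TEAE.

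TEAEs by maximum severity are a planned display in Protocol 9.5 and SAP 5.5.12. Protocol 9.5.1 and SAP 5.5.12.1 apply Fisher's exact test to categorical safety measures in Study Period III. If the literal rule is programmed, some patients whose only new event was mild will be counted as moderate or severe on the strength of an event that did not emerge on treatment. Two programmers could also produce different tables from the same text.

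**Working it through.** The documents give no figure to reproduce, so the check applies the written rule to cases.

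**Inputs.** The grades are mild, moderate and severe (Protocol 9.5.2), coded here as 1, 2 and 3, with 0 for no record; the coding is mine. For LLT *i*, b(i) is the baseline maximum and p(i) the post-baseline maximum. The periods come from SAP Table 5.5.

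**Rules.**
- Emergent: p(i) > b(i).
- Literal display: L = maximum of p(i) over all LLTs under the term.
- Restricted display: R = maximum of p(i) over the emergent LLTs only.

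The emergent LLTs are a subset of all LLTs, so L ≥ R always. A patient enters the table only if at least one LLT emerged, which is the same under both rules, so TEAE incidence does not change.

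**Cases.** Each adds a new mild LLT (b = 0, p = 1) under the same term.

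| Other LLT | b, p | L | R |
|---|---|---|---|
| Severe at baseline, recurs as severe | 3, 3 | severe | mild |
| Severe at baseline, recorded as improved to moderate | 3, 2 | moderate | mild |
| Severe in Period III, recurs as severe in Period IV (baseline is Visits 1 to 12) | 3, 3 | severe | mild |
| Severe at baseline, no post-baseline record | 3, 0 | mild | mild |

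The last row marks the limit: without a post-baseline severity on record, the two rules agree.

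**Count of two-LLT patterns.** Each LLT has 4 × 4 = 16 (b, p) pairs, of which 6 are emergent and 10 are not. Patterns with at least one emergent LLT: 16² − 10² = 256 − 100 = 156.

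The rules differ only when one LLT is emergent and the other is non-emergent with a higher p:
- Emergent p = 1 occurs in 1 way. A non-emergent LLT with p = 2 occurs in 2 ways and with p = 3 in 1 way. That gives 1 × (2 + 1) = 3.
- Emergent p = 2 occurs in 2 ways. A non-emergent LLT with p = 3 occurs in 1 way. That gives 2 × 1 = 2.
- Emergent p = 3 cannot be exceeded.

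The sum is 5. Either LLT can be the emergent one, so 2 × 5 = 10 of the 156 patterns differ, all upward. These are possible patterns with equal weight; they say nothing about how many patients would show them.

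**Level.** A PT gathers few, closely related LLTs, while a SOC gathers many unrelated ones. The chance that a non-emergent LLT shares a term with a milder new one is therefore greatest at SOC level.

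**The case against.** The best defence is that the narrower rule is already meant. The general sentence is framed by patient and TEAE, it follows directly after the emergence test, and *associated* LLTs may mean those that make up the TEAE. That reading is open. It is not secured, because the words that follow define the set by mapping to the MedDRA level, and the two SAP subsections state the rule without the term TEAE.

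A reader might go further and infer that any unchanged severe pre-existing condition will make a new mild event display as severe, and that this will be common because Protocol 8.2 has such conditions recorded. The documents do not support that. Protocol 8.2 records changes and new conditions as adverse events; nothing in either document says that an unchanged condition carries a severity into the post-baseline period. Without such a record the display is the same under both rules.

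A reader might also infer that the rule hides a real difference between arms, or inflates placebo more than active treatment. Either would need the share of TEAE patients in each arm who have a higher non-emergent LLT under the same term. The documents give no such share, and the rule is identical in every arm.

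Other points stand in the plan's favour. The severity tables whose level is named (hypersensitivity, injection-site events, upper respiratory infections) are at PT level, where overlap is least likely, and SAP 5.5.12 lists SOC and maximum severity as separate items. Serious events and events leading to discontinuation have their own displays. Any error over-reports severity and hides no event.

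**Conclusion.** The point holds as a gap in a derivation rule, and it is minor. As written, the displayed severity is not limited to treatment-emergent LLTs in any of the four sections, and no other section narrows it. Followed literally, the rule overstates severity when a non-emergent LLT has a higher post-baseline grade on record than the emergent LLTs under the same term. The overstatement is always upward, can reach two grades (mild shown as severe), and leaves TEAE counts unchanged.

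This rests on two conditions: that the literal reading is what gets programmed, and that such non-emergent post-baseline records exist. Recurrence at the same grade, recorded partial improvement, and recurrence in Period IV of a Period III event can each produce them under the documents' own recording and baseline rules. How often they occur cannot be derived from the documents.

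**What to change.** Insert *treatment-emergent* before the reference to Lowest Level Terms in Protocol 9.5.2, and before the reference to LLTs in SAP 5.5.12.1.1, 5.5.12.1.1.2 and 5.5.12.1.1.3. In the table program, keep only the LLTs flagged as emergent for that patient in the period being tabulated (Period III against Visits 1 to 3, Period IV against Visits 1 to 12) before taking the maximum.

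The change will matter little for injection-site events. In Period III it would need such an event on record at baseline, before any study injection; in Period IV it would need a recurrence after dosing has ended.

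The cost is one word per section and one filter. The SAP states that it supersedes the protocol's statistical plans, so the SAP text is the one that governs the tables. Protocol 9.2 lets a change of this kind be described in the SAP before unblinding, or in the study report, without an amendment. If the narrower rule is already intended, no result changes and the ambiguity is gone.
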